5.3.3.10 Electrocardiogram (ECG)

Summaries of evaluation (normal; abnormal not clinically significant; abnormal clinically significant) will be provided by treatment arm and overall for post-baseline measurements (End of Treatment Period (Day 169 or ET).

All ECG results will be listed on a by-patient basis.

5.3.3.11 Vital Signs and Height, weight, and BMI

A summary of vital signs (including systolic and diastolic blood pressure and body temperature (in °C), heart rate and respiratory rate) including change from baseline (where appropriate), presented by descriptive statistics, will be displayed by treatment arm and overall, for each visit day from baseline through Day 169. Particularly, for vital signs measured after first and second doses, the maximum value among all values recorded in the 2 hours post-dosing will be taken as the representative for that day in summaries by visit.

Vital Signs data during the treatment period will be summarized in the current visits: Day 1, 8, 29, 36, 57, 85, 113, 141 and 169. Visits Day 64, Day 92, Day 120 and Day 148 for collection of Vital Signs data during the treatment period were removed in the protocol version for which this SAP version is planned.

For patients following previous versions of the protocol, data recorded on the days of the current visits listed above will be used for analyses. Only if there is no data collected in these visits and these patients have additional values in visits previously collected, those data will be used for analyses following the correspondence: Day 64 to Day 85; Day 92 to Day 113; Day 120 to Day 141; Day 148 to Day 169.

In addition, a summary and change from pre-dose of the values measured in the 2 hours post-dose (at 15 minutes intervals) after the first and second doses will be presented using the maximum value among

all values recorded in the 2 hours post-dosing. Pre-dose will be the latest assessment prior to the dose being summarized.

Height, weight, and BMI and the corresponding change from baseline will be summarized for visits after baseline.

Only available data will be used, and missing data will not be imputed. Change from baseline and predose will be calculated only for patients with non-missing values for both the baseline or pre-dose and the time-point of interest and will be missing otherwise.

Vital Signs (on dosing and no-dosing days) and height, weight and BMI after baseline will be listed.

5.3.3.12 Laboratory Evaluation

Hematology (including white blood cells (WBC), red blood cells, hemoglobin, hematocrit, mean corpuscular volume, mean corpuscular hemoglobin, mean corpuscular hemoglobin concentration, platelets, WBC differential (absolute and %), neutrophils, lymphocytes, monocytes, eosinophils, basophils); Liver Panel (including total and direct bilirubin, AST, ALT, total protein, albumin, GGT, lactate dehydrogenase, AP, INR); Serum Chemistry (including sodium, potassium, urea, creatinine, calcium, phosphate, glucose, creatine kinase) will be evaluated at each scheduled visit day during treatment period, as well as the scheduled days during Treatment follow-up period.

Urinalysis (including protein, bilirubin, urobilinogen, ketones, glucose, leukocyte esterase, red blood cells, pH, nitrites, specific gravity, microscopy) will only be evaluated in the same days during treatment period but not during the Treatment follow-up period.

The summary statistics (including number, mean, SD, median, Q1, Q3, minimum, and maximum) of all quantitative laboratory variables (laboratory values and changes from baseline) will be calculated for each dose during the treatment period and for each visit during the follow-up period, by treatment arm.

Laboratory data will be analyzed at pre-doses of Dose 1 to 6. For all parameters, the last available measurement after last dose and before the current dose will be the representative value to be summarized for each dose (ie: for dose 2, last value taken from "Date of dose 1 + 1 day until Date of dose 2").

For each visit during the follow-up period, the last of all measurements for the corresponding visit will be the representative value to be summarized.

The number (%) of patients with abnormal results (out of normal range) for each of the laboratory variables will be summarized at pre-dose of Doses 1 to 6 and in each visit during the follow-up period and treatment arm

22-Apr-2024

Shift tables for baseline versus each pre-dose for Doses 1 to 6 and follow-up visits will be presented for the hematology, urinallysis and chemistry laboratory parameters.

Data collected for Microscopy in Urinalysis (if clinically indicated or hemoglobin is detected on dipstick) will only be listed.

Data will be listed by patient.

Only available data will be used, and missing data will not be imputed.

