- 1 If an authorized COVID-19 vaccine has been administered in proximity to a scheduled IP administration, a ± 3 day window is allowed for IP dosing.
- ^m After Day 169 or ET, only MAEs, NCIs and IMCs will be recorded.
- ⁿ A single blood sample will be collected for biobanking at the beginning of the study (prior to dosing on Day 1) and end of the study. This sample will be used for future analyses not specified in the protocol. Analysis will be limited to HBV serologic and HBV-specific DNA and RNA and patients' DNA will not be analyzed.
- ° Safety laboratory testing, including liver panel, for Doses 1 and 2 will be obtained during the visits conducted 7±2 days after these doses of study medication. Safety laboratory testing following Doses 3, 4 and 5 will be obtained in the interval from 7 days after dose administration and before the next dose of study medication is administered. Safety labs after Dose 6 will be assessed at the Day 169 visit.
- ^p Diaries will also be reviewed at the Day 85, Day 113, Day 141 and Day 169 visits

Table 2 Schedule of Events – Follow-up Period

	Follow-Up Period					
Study Visit	Day 232	Day 323	Day 414	Day 505 or ET ^a		
Completion of Week (number)	33	46	59	72		
Window (days)	±10 days	±10 days	±10 days	±10 days		
Visit may be conducted at home or work or in part as a telemedicine visit ^b	X		X			
Immunosuppressive medications, vaccines, and new HBV treatments (only) ^c	X	X	X	X		
Targeted and symptom-driven PE	X	X	X	X		
Height and weight				X		
Vital signs ^d	X	X	X	X		
ECG ^d				X		
Hematology and serum chemistry	X	X	X	X		
Liver panel	X	X	X	X		
HBV serology and viral markers ^e		X		X		
Whole blood for PBMC isolation		X		X		
MAEs, NCIs and IMCs (only) ^f	X	X	X	X		

AE = adverse event; ECG = electrocardiogram; ET = early termination; HBV = hepatitis B virus; HIV = human immunodeficiency virus; MAE = medically-attended adverse event; NCI = new-onset chronic illness; IMC = immune-mediated medical condition; PBMC = peripheral blood nonnuclear cell; PE = physical examination.

^a If a patient prematurely discontinues study medication before Day 505, Day 505/Early termination procedures will be performed.

^b A telemedicine visit would include a home visit by appropriate trained personnel to perform a target and symptom-driven physical and obtain vital signs and safety laboratories. The remaining portions of the visit may be conducted virtually by the study investigator.

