10.4.3. Analysis of Safety

Quantitative safety data will be summarized using descriptive statistics and frequency distributions. Qualitative safety data will be summarized by frequencies and percentages. All summaries will be presented by treatment arm. AEs will be coded using Medical Dictionary for Regulatory Activities (MedDRA) and concomitant medications will be coded using WHO drug dictionary.

Laboratory evaluations, vital signs assessments and ECG parameters will be summarized by treatment group and protocol specified collection time point. A summary of change from baseline at each protocol specified time point by treatment group will also be presented.

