14.2.2.4.1	Summary and change from baseline of IFN-γ	mITT Population	Yes	
	frequency by ELISpot assay in PBMCs: Days 85			
	and 169			
14.2.2.4.2	Non-Parametric Model for IFN-γ frequency by	mITT Population	Yes	
	ELISpot assay in PBMCs: Days 85 and 169			
14.3. Safety Da	ta Summary Tables			
14.3.1. Adverse	Events			

22-Apr-2024

TFL Number	Title	Analysis Set	Included in	TOP LINE
			Final report	TABLES
14.3.1.1	Overall Summary of Treatment Emergent Adverse	Safety Population	Yes	V
	Events			
14.3.1.2	TEAEs by System Organ Class and Preferred	Safety Population	Yes	
	Term			
14.3.1.3	TEAEs by Preferred Term	Safety Population	Yes	
14.3.1.4	TEAEs related to study drug by System Organ	Safety Population	Yes	
	Class and Preferred Term			
14.3.1.5	TEAEs related to study drug Grade 3 or higher by	Safety Population	Yes	
	System Organ Class and Preferred Term			
14.3.1.6	TEAEs by maximum severity by System Organ	Safety Population	Yes	
	Class and Preferred Term			
14.3.2 Serious	Adverse Events		·	
14.3.2.1	Serious TEAEs by System Organ Class and	Safety Population	Yes	
	Preferred Term			
14.3.2.2	TEAEs leading to study drug permanently	Safety Population	Yes	
	discontinued by System Organ Class and			
	Preferred Term			
14.3.3 Other Ad	lverse Events		·	
14.3.3.1.1	Medically-Attended AEs (MAEs) by System Organ	Safety Population	Yes	
	Class and Preferred Term. Treatment Period			
14.3.3.1.2	Medically-Attended AEs (MAEs) by System Organ	Safety Population	Yes	
	Class and Preferred Term. Follow-Up Period			
14.3.3.2.1	New-onset Chronic Illnesses (NCIs) by System	Safety Population	Yes	
	Organ Class and Preferred Term. Treatment			
	Period			
14.3.3.2.2	New-onset Chronic Illnesses (NCIs) by System	Safety Population	Yes	
	Organ Class and Preferred Term. Follow-Up			
	Period			

TFL Number	Title	Analysis Set	Included in Final report	TOP LINE TABLES
14.3.3.3.1	Immune-mediated Medical Conditions (IMCs) by System Organ Class and Preferred Term. Treatment Period	Safety Population	Yes	
14.3.3.3.2	Immune-mediated Medical Conditions (IMCs) by System Organ Class and Preferred Term. Follow- Up Period	Safety Population	Yes	
14.3.4 Clinical I	_aboratory Tests			
14.3.4.1.1	Summary of pre-dose Values and Change from baseline for Clinical Laboratory Hematology Results	Safety Population	Yes (Through D169)	
14.3.4.1.2	Summary of Abnormalities for Clinical Laboratory Hematology Results	Safety Population	Yes (Through D169)	

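### SAP 5.3.3.12 defines no laboratory timepoint between a patient's last dose and Day 169/ET, and contradicts itself on whether those samples are tabulated

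*SAP*

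**What the plan says.** The Protocol (10.4.3) plans that laboratory evaluations "will be summarized by treatment group and protocol specified collection time point". Table 1 of the Protocol schedules safety laboratory tests and the liver panel at Day 169, and its footnote adds that "Safety labs after Dose 6 will be assessed at the Day 169 visit".

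SAP 5.3.3.12 opens in the same spirit: hematology, liver panel and chemistry are evaluated at every scheduled visit day of the treatment period and of follow-up. The operative sentences then narrow this.

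- Summary statistics: "Laboratory data will be analyzed at pre-doses of Dose 1 to 6", where "the last available measurement after last dose and before the current dose will be the representative value to be summarized for each dose". The worked example for Dose 2 runs from the day after Dose 1 to the date of Dose 2.
- Abnormal results: "will be summarized at pre-dose of Doses 1 to 6 and in each visit during the follow-up period".
- Shift tables: "Shift tables for baseline versus each pre-dose for Doses 1 to 6 and follow-up visits will be presented".
- Follow-up: "For each visit during the follow-up period, the last of all measurements for the corresponding visit will be the representative value to be summarized".

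SAP Appendix 1 lists ten laboratory tables, 14.3.4.1.1 to 14.3.4.3.4. The six hematology and biochemistry tables are marked as running through Day 169. Three of the ten have pre-dose values in the title, for example "Summary of pre-dose Values and Change from baseline for Clinical Laboratory Hematology Results". SAP 5.3.17, on changes from the protocol-planned analyses, mentions only the ECG parameters.

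**The concern.** A pre-dose slot needs a following dose. After a patient's last dose there is none, so the window that picks the value cannot be formed, and no end-of-treatment or early-termination slot takes its place.

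Two groups of samples are affected. The Day 169 sample in completers is the only scheduled safety laboratory look after the sixth dose, at full cumulative exposure. In patients whose dosing ends early, the gap covers the panels between the last dose and early termination. Those can include the result that led to stopping, because the Protocol interrupts or ends dosing on ALT, AST, bilirubin and INR findings (4.1, 6.4, 7.1.1). Changes in these parameters are a named safety endpoint (Protocol 3.4; SAP 4.3). If the slot rule is programmed as written, the tables for that endpoint omit end-of-treatment values for everyone and post-last-dose values for the patients in whom they may matter most.

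**Working it through.** The plan gives no figure to reproduce. The check applies the written slot rule to the schedule and then compares the conflicting texts.

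**Inputs**
- Dose days 1, 29, 57, 85, 113, 141 (Protocol 6.3).
- Laboratory days 1, 8, 29, 36, 57, 85, 113, 141, 169 (Protocol Table 1; screening left out).
- Slot j takes the last value from the day after dose j − 1 to the day of dose j (SAP 5.3.3.12); slot 1 takes the last value up to Day 1.
- Follow-up visits at 13, 26, 39 and 52 weeks after the last dose (Protocol 7.1; SAP section on withdrawals). For completers these are Days 232, 323, 414 and 505 (Protocol Table 2).
- Assumption for early stoppers: the next planned pre-dose sample is drawn and the dose is then withheld.

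**Step 1, completer.** Slots 1 to 6 take Days 1, 29, 57, 85, 113 and 141. Day 169 lies after Dose 6 and no seventh dose exists, so no slot takes it. Slots 2 to 6 represent the intervals after Doses 1 to 5, that is 5 of 6; the missing share is 1/6 = 16.7%. (Days 8 and 36 lie inside a window but give way to a later value there. That is a different matter.)

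**Step 2, k doses received.** Slot 1 is baseline and slots 2 to k represent k − 1 of the k post-dose intervals. The first follow-up visit is nominally at the last dose day + 13 × 7 = + 91 days.

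| Doses received (k) | Scheduled samples without a slot | Intervals represented | First follow-up visit |
|---|---|---|---|
| 1 | Days 8, 29 | 0 of 1 | Day 92 |
| 2 | Days 36, 57 | 1 of 2 | Day 120 |
| 3 | Day 85 | 2 of 3 | Day 148 |
| 4 | Day 113 | 3 of 4 | Day 176 |
| 5 | Day 141 | 4 of 5 | Day 204 |
| 6 | Day 169 | 5 of 6 | Day 232 |

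For k below 6, the early-termination panel and any weekly liver panels after the last dose also have no slot. Values up to the last dose keep theirs.

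**Step 3, texts that might supply the missing slot**
- The opening sentence of 5.3.3.12 covers Day 169 as a scheduled visit, but the three sentences that define the tabulated timepoints do not carry it through.
- The index note implies that Day 169 belongs in six tables, but the text gives no rule for filling such a column. The four urinalysis tables carry no such note.
- The SAP's study schematic starts follow-up after the Week 20 dose, which would put Day 169 inside it. Yet Day 169 is in the treatment schedule (Protocol Table 1), Table 2 begins at Day 232, and SAP 5.3.3.10 calls Day 169/ET the end of the treatment period. This reading would also exclude Day 169 urinalysis, since 5.3.3.12 does not evaluate urinalysis in follow-up.

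**Step 4, neighbouring sections.** The SAP names Day 169 for physical examination (5.3.3.9), ECG (5.3.3.10) and vital signs (5.3.3.11, which also maps legacy Day 148 data to Day 169). Laboratory data lack an equivalent.

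**The case against.** The strongest reply is that the SAP, read as a whole, intends Day 169 to be tabulated. The section's opening sentence and the index both point that way, and the abnormality and shift tables do not have pre-dose in their titles. This stands to the extent that one cannot say Day 169 will certainly be missing. It does not settle the matter, because the sentences a programmer would follow still define no such timepoint.

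A reader might also infer that all laboratory data of patients stopped for toxicity vanish and that the tables are therefore biased toward showing no liver effect. The documents do not support that:
- Values up to the last dose remain in their slots, and follow-up visits have a slot in the text. The follow-up slot is less secure than it looks: the index ends the hematology and biochemistry tables at Day 169, and the termination addendum adds follow-up tables only for MAEs, NCIs and IMCs.
- A patient whose dosing is interrupted and restarted has a later dose, so the slot is filled. Some ALT/AST elevations do not interrupt dosing under Protocol 4.1.
- In completers the Day 169 gap falls on both arms and does not depend on the result.
- Flares are counted from all treatment-period ALT values (SAP 4.3). Clinically significant, confirmed laboratory abnormalities are recorded as adverse events (Protocol 9.4) and so reach the TEAE tables, including 14.3.2.2 where they end dosing. All laboratory values are listed.

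These routes recover part of the signal. They do not replace by-arm tables of bilirubin, INR, AST, blood counts and ALT below flare level after the last dose.

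**Conclusion.** The point holds as a faulty slot rule that conflicts with its own section, with the table index and with the Protocol's plan, and that is not declared in SAP 5.3.17. Applied as written, it leaves one of six post-dose intervals (16.7%) empty for every completer and k − 1 of k represented for a patient with k doses.

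These figures count slots; they are not an effect size. The early-stopper rows rest on the nominal schedule and on the assumption about the next pre-dose draw. The documents do not say how many patients stopped early or why, and SAP section 2 reports no significant safety events, so the size or even the presence of bias from early stopping cannot be stated. The Day 169 gap does not depend on that number. No test or error rate is affected, as the laboratory analysis is descriptive.

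**What to change.** In SAP 5.3.3.12, add a treatment-period timepoint labelled as post-last-dose, Day 169 or ET. Define it as the last value after the patient's final dose through the Day 169/ET visit, with any legacy Day 148 laboratory data mapped to it as is done for vital signs. Apply it to Tables 14.3.4.1.1 to 14.3.4.3.4 and align the three pre-dose table titles. State whether the follow-up slot in the text is still to be tabulated, given the Day 169 limit in the index. If any of these samples are deliberately left out, say so in 5.3.17.

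Optionally, the abnormality and shift tables could also show the worst value after the last dose, including unscheduled panels. That goes beyond closing the gap.

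The cost is a wording change, one extra column and a re-run of the tables, some of which were already produced for the Week 24 analysis. No new data are needed.

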4.6. Schedule of Events

The schedule for study activities is presented in Table 1 for the Screening and Treatment Periods and in Table 2 for the Follow-up Period.

 Table 1
 Schedule of Events – Screening and Treatment Periods

Schedule of Ever	Screening Period Treatment Period									
Study Day		Telephone Visit (if needed) ^a	Day 1	Day 8, 36	Day 29	Day 57	Day 85	Day 113	Day 141	Day 169 or ET ^b
Week (s)	-4 to -1		0	7 days after prior visit	4	8	12	16	20	24
Window (days)	_	Up to 3 working days before Day 1	_	±2 days	±2 days	±2 days	±2 days	±2days	±2 days	±2 days
Dose of study medication			1		2	3	4	5	6	
Visit may be conducted at home or work or in part as a telemedicine visit ^c				X						
Informed consent	X									
Eligibility criteria check	X	X	X							
Demographics	X									
Medical history	X									
Concomitant medications (including immunosuppressive medications, vaccines, and new HBV treatments) ^d	X	X	X	X	X	X	X	X	X	X
Complete PE	X									X
Targeted and symptom-driven PE	71		X	X	X	X	X	X	X	11
Height, weight, and BMI	X									X
Vital signs ^e	X		X	X	X	X	X	X	X	X
Fibroscan ^f	X									
ECG e	X									X
Urine pregnancy test ^g	X		X		X	X	X	X	X	X
Drug and alcohol screen	X									
Hepatitis B genotype h	X									
HCV, HDV, and HIV tests	X									
Safety labs °	X		X	X	X	X	X	X	X	X
Liver panel °	X		X	X	X	X	X	X	X	X
HBV serology and viral markers i	X		X				X			X
Whole blood for PBMC isolation			X				X			X
Randomization		Xª	X							
Study medication administration (number)			1		2 j,k,l	3 j,k,l	4 j,k,l	5 j,k,l	6 ^{j,k,l}	
Diary distribution (D) review (R) p			D	R	D	D	RD	RD	RD	R

Screening Period		Treatment Period								
Study Day	Day -35 to Day -4	Telephone Visit (if needed) ^a	Day 1	Day 8, 36	Day 29	Day 57	Day 85	Day 113	Day 141	Day 169 or ET ^b
AEs, including MAEs, NCIs and IMCs, and reactogenicity (systemic and local) ^m	X	X	X	X	X	X	X	X	X	X
Stored blood sample for future analyses ⁿ			X							X

AE = adverse event; BMI = body mass index; ECG = electrocardiogram; ET = early termination; HBV = hepatitis B virus; HCV = hepatitis C virus; HDV = hepatitis delta virus; HIV = human immunodeficiency virus; MAE = medically-attended adverse event; NCI = new-onset chronic illness; IMC = immune-mediated medical condition; PBMC = peripheral blood nonnuclear cell; PE = physical examination; UA = urinalysis

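### The SAP's lab tables can omit the Day 8 and Day 36 safety labs and have no stated Day 169 row, and its vital-sign tables after Doses 1 and 2 show only the 2-hour maximum

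*SAP*

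**What the plan says.** **Laboratory data.** SAP 5.3.3.12 opens by stating that hematology, liver panel and chemistry "will be evaluated at each scheduled visit day during treatment period". It then ties the treatment-period tables to the pre-dose point of Doses 1 to 6: "the last available measurement after last dose and before the current dose will be the representative value to be summarized for each dose". Its worked example runs the Dose 2 window from the day after Dose 1 through the date of Dose 2. The counts of out-of-range results use the same points, and so do the shifts: "Shift tables for baseline versus each pre-dose for Doses 1 to 6 and follow-up visits will be presented". The section ends with "Data will be listed by patient".

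**Lab schedule.** Protocol Table 1 ("Schedule of Events – Screening and Treatment Periods") marks safety labs and liver panel at every treatment-period visit, including Days 8 and 36. Footnote o names those two visits as the ones that supply the safety labs for Doses 1 and 2, and Day 169 as the visit for Dose 6.

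**Vital signs.** After the first two doses the protocol takes readings every 15 minutes for 2 hours. SAP 5.3.3.11 reduces these to one number: "the maximum value among all values recorded in the 2 hours post-dosing will be taken as the representative for that day". The change-from-pre-dose table uses the maximum as well. No minimum is planned. The same section gives Day 169 its own place and remaps removed visits to current ones ("Day 120 to Day 141; Day 148 to Day 169"); the lab section has no equivalent rule. Vital signs are also listed: "Vital Signs (on dosing and no-dosing days) and height, weight and BMI after baseline will be listed".

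**What the protocol promised.** Protocol 10.4.3 plans lab and vital-sign summaries at each collection time point in the protocol. SAP 5.3.17 declares only that ECG parameters are unavailable.

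**The concern.** Safety is a secondary objective, and changes in liver tests, INR and other laboratory parameters are a named safety endpoint (Protocol 3.4). Days 8 and 36 are the visits placed about a week after Doses 1 and 2 to look for early effects. A last-value rule favours the sample furthest from the dose, so an early change that resolves by Day 29 or Day 57 would not appear in any laboratory table.

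Day 169 is the only scheduled lab after Dose 6. It is neither a pre-dose point nor one of the Table 2 follow-up visits (Days 232, 323, 414 and 505), so the 5.3.3.12 text leaves it without a row.

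For vital signs, Protocol 8.3.6 names five kinds of change for grading: tachycardia, bradycardia, hypertension, hypotension and fever. A maximum can reveal three of them. It cannot reveal bradycardia or hypotension unless the fall lasts through every reading. It also makes an unchanged patient look as if the value rose.

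**Working it through.** The plan states no figure on this point, so there is none to reproduce. The check applies the SAP's rules to the protocol's nominal schedule.

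**1. Labs, Table 1 read at face value.** Dose days are 1, 29, 57, 85, 113 and 141 (Protocol 6.3). Post-baseline treatment-period lab days are 8, 29, 36, 57, 85, 113, 141 and 169, which is 8 visits (Table 1). The window for each dose runs from the day after the previous dose through the current dose date.

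| Row | Window (nominal days) | Labs inside | Value tabulated |
|---|---|---|---|
| Dose 2 | 2–29 | 8, 29 | 29 |
| Dose 3 | 30–57 | 36, 57 | 57 |
| Dose 4 | 58–85 | 85 | 85 |
| Dose 5 | 86–113 | 113 | 113 |
| Dose 6 | 114–141 | 141 | 141 |

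Days 8 and 36 are displaced: 2/8 = 25% of visits. With 80 patients and full attendance (assumed), that is 80 × 2 = 160 of 80 × 8 = 640 patient-visits. Where a Day 29 or Day 57 sample is absent, the Day 8 or Day 36 value is used instead. Day 169 is not counted as displaced, because the index tags the hematology and biochemistry tables as running through Day 169. That is a contradiction between text and index, not a demonstrated loss.

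**2. Labs, footnote o read as the whole schedule.** The labs are then Day 8, Day 36, one draw in each interval after Doses 3, 4 and 5, and Day 169: 6 in all, with none displaced. But 29 − 8 = 21 and 57 − 36 = 21, so 2 of the 5 post-baseline pre-dose rows (Doses 2 and 3) hold values drawn nominally 21 days before the dose.

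**3. Vital signs.** 120 min / 15 min = 8 post-dose readings. The maximum rule touches Days 1 and 29, which are 2 of the 9 days listed in SAP 5.3.3.11 (1, 8, 29, 36, 57, 85, 113, 141, 169).

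The documents give no reading-to-reading SD, so call it s and assume independent normal readings.

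- With no true change, the expected change from pre-dose using the maximum is the expected maximum of 8 standard normals times s, or 1.4236s.
- If pressure falls 20 mmHg in 4 of the 8 readings, the maximum comes almost entirely from the other 4, so it is about 1.0294s. The minimum is about −(20 + 1.0294s). Simulation with 400,000 patients per value of s agrees with both.

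| Assumed s (mmHg) | No change: maximum shows | 20 mmHg fall in 4 of 8: maximum shows | Same fall: minimum would show |
|---|---|---|---|
| 3 | +4.3 | +3.1 | −23.1 |
| 5 | +7.1 | +5.1 | −25.1 |
| 8 | +11.4 | +8.2 | −28.2 |

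A 20 mmHg fall at a single reading, with s = 5, moves the mean tabulated maximum only from 7.11 to 6.76, while the mean minimum is about −20.

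**The case against.** The strongest reply is that nothing leaves the report. Every lab and vital-sign value is listed. Hepatitis flares use every ALT measurement (SAP 4.3). Clinically relevant changes are recorded as AEs (Protocol 8.3.6 and 9.4) and tabulated by arm. The upward shift from the maximum is common to both arms, so it does not by itself bias the comparison. The SD, the independence and the pattern of the fall are all assumed. The 2-of-8 count is idealised, because patients under earlier protocol versions attended extra visits. Protocol 10.6 lets the SAP supersede the protocol on all but the primary analysis, so the departure from 10.4.3 is allowed. All of this stands. It limits the point to the tabulated between-arm comparison and an undeclared, though permitted, change. It does not answer the point: the flare route requires ALT of at least 3 × ULN, and listings and investigator judgment do not compare arms on bilirubin, INR, AST, hematology or smaller ALT changes.

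A reader might go further and infer three things that the documents do not support.

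- *That a result which holds back a dose never reaches a table.* The window includes the dosing day. A Day 29 sample reported after Dose 2 has been given, and which then delays Dose 3, is in the Dose 2 row. Lab turnaround is not stated, so no general rule follows.
- *That patients who stop dosing lose all later lab rows.* They stay for follow-up visits (Protocol 7.1), and the 5.3.3.12 text tabulates hematology, liver panel and chemistry at those visits. What that text omits is their Day 169/ET row. The index tag may remove the follow-up rows too, which is one more reason to reconcile it with the text.
- *That the window and maximum rules were adopted after the interim results were known.* The SAP history for version 2.0 mentions the non-parametric model, minor issues and modified tables. It does not date these rules.

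**Conclusion.** The point holds as a reporting gap in the safety tables. It does not touch the primary analysis, and no data are lost. On the Table 1 schedule, 2 of 8 post-baseline treatment-period lab visits drop out of the summary, abnormality and shift tables whenever the later sample exists. On the footnote o reading the figure is 0, with two rows mislabelled by about 21 days. The Day 169/ET lab row is unresolved between text and index. The maximum rule cannot show 2 of the 5 vital-sign events named for grading when they are transient. It adds about 1.4 within-session SDs to the change from pre-dose in both arms, if the 8 readings are independent and normal.

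The criticism does not extend to the window for labs that follow Doses 3 to 5, since Protocol 4.3 lets those be drawn at any time from 7 days after the dose until the next one. SAP 2.3 describes labs about a week after every dose. That is best read as wording left over from the removed Day 64, 92, 120 and 148 visits, and needs only a clean-up. Separately, Protocol 4.1 allows dosing to restart after some liver-test abnormalities, while Protocol 6.4 and SAP 5.3.16 end dosing permanently for Stopping Rule events. Those passages must be reconciled, but this point does not depend on them.

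**What to change.** 1. Add Day 8, Day 36 and Day 169/ET rows, labelled by visit, to the lab summary, abnormality and shift tables, including urinalysis. Keep the per-dose window for labs after Doses 3 to 5.
2. For blood pressure and pulse after Doses 1 and 2, report the 2-hour minimum beside the maximum.
3. Optionally, add one table of each patient's worst post-baseline treatment-period lab value, including unscheduled tests. It would raise abnormality counts in both arms and should be read as such.
4. Reconcile the lab schedule wording in Protocol Table 1, footnote o and SAP 2.3, and Day 169 between SAP 5.3.3.12 and the Appendix 1 index.
5. In SAP 5.3.17, declare the window and maximum rules as departures from Protocol 10.4.3, permitted by 10.6, without assigning them a date. Date only the new tables and rows as made after the Week 24 interim analysis.

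The cost is programming only: rows in up to 10 laboratory tables (3 hematology + 3 biochemistry + 4 urinalysis), a minimum column in 2 vital-sign tables (14.3.7.1 and 14.3.7.2), and the optional table. No new data are needed. The additions would be supplementary and post hoc, since the Week 24 tables already exist. Because the product will not be tested further, the gain is a complete safety report rather than a change to a later trial.
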